2. AMENDMENT HISTORY

3. SYNOPSIS

Study Title	Duodenal-jejunal bypass liner (EndoBarrier [™]) in obese subjects with type 2 diabetes: Impact on pancreatic function, insulin resistance, gut peptides and gut permeability						
Study Design	Open, single-centre, single-arm pilot study						
Study Participants	Obese, adult, type 2 diabetic subjects with suboptimal glycaemic control and a BMI between 30 and 49 kg/m ² .						
Number of Participants	12						
Follow-up duration	15 months						
Planned Duration	30 months						
Primary Objective	The primary aim of the study is to explore short and long-term effects of the EndoBarrier [™] implantation on insulin resistance and beta-cell function assessed by repeated Botnia clamps.						
Secondary Objectives	In addition we will determine the changes in gut peptides and gut permeability after implantation of a removable duodeno-jejunal bypass device in obese subjects with sub-optimally controlled type 2 diabetes. Further we aim to investigate the changes in body weight, body composition, gut microbiota and the change in global cardiovascular risk from baseline to 9 months, estimated using the UKPDS risk engine.						

4. BACKGROUND AND RATIONALE

Obesity has reached epidemic proportions in the western world and has risen to the top of the public health policy agenda. The World Health Organisation (WHO) predicts that by 2015 approximately 2.3 billion adults will be overweight (BMI 25-29.9 kg/m²), and more than 700 million will be obese (BMI 30 kg/m² or more)(1).

In 2007, more than 40% of Austrian adults were either overweight or obese (11%) and the proportion of overweight people is projected to rise even further over the next 10 years (2).

The association between obesity and type 2 diabetes mellitus (T2DM) is well recognised. A higher body mass index (BMI) is a strong predictor of T2DM (3).

Currently, 285 million people suffer from type 2 diabetes, and this number is predicted to increase to 439 million by 2030 (4). T2DM raises the risk for cardiovascular events, heart failure, eye problems, and kidney diseases. The International Diabetes Federation (IDF) report 2012 predicts that diabetes will strike one in ten adults by 2030 (5). Previous research has demonstrated that the impact of diabetes on everyday life and the likelihood of costly and disabling complications can be minimized by more intensive management of glucose (6), blood pressure (7) and cholesterol (8).

Bariatric surgery (BS) has been established as a treatment option for morbidly obese patients or obese subjects with comorbidities such as T2DM. Bariatric surgery, besides reducing body weight, has been reported to improve glycaemic control in patients with T2DM and importantly to reduce cardiovascular events and overall mortality in obese subjects (9-12).

Interestingly, the degree of improvement in hyperglycaemia or reductions in rates of cardiovascular events or mortality do not appear to be directly associated with the amount of weight loss, suggesting a role for other mechanisms (11-13).

A crucial observation is that glycaemic improvement occurs rapidly, within the first weeks after BS, and cannot be explained by the relatively small weight loss seen during this short time period. These beneficial glycaemic changes after bypass procedures have been attributed to changes in incretin levels and other gut hormones (14). The more rapid stimulation of the distal ileum following operative exclusion of the duodenum and the proximal jejunum has been suggested as an explanation for the hormone changes observed (15). However, the definitive mechanisms leading to the rapid improvement in glycaemia or even remission of diabetes after BS have yet to be clarified.

Though, surgical interventions are irreversible and not free of complications. In some cases they require re-surgery or endoscopic procedures to correct problems such as fistulas etc. have to be performed (16). Additionally, operative therapies are not suitable for all obese patients or are not well accepted by all operative candidates.

Recently a duodenal-jejunal bypass sleeve (EndoBarrier[™] Gastrointestinal Liner; GI Dynamics, Inc., Lexington, MA, USA) has been introduced. The EndoBarrier[™] is a 60 cm long impermeable fluoropolymer sleeve-like device that is placed endoscopically via the mouth and anchored in the duodenum to create a duodenal-jejunal bypass for up to 12 months. It allows transit of chyme from the stomach through to the jejunum without any contact with the duodenal wall. By not allowing mixing with bile and pancreatic exocrine secretions in the proximal jejunum, it mimics a duodenal-jejunal bypass and therefore induces weight loss.

A number of small studies have demonstrated the feasibility of implanting this device with subsequent weight reduction (17-19). In obese T2DM subjects a significant improvement in glycaemic parameters after EndoBarrier[™] implantation has been observed (20) and a small randomised one-year study in 18 T2DM subjects with sham endoscopy as the comparator, demonstrated superiority of the liner in terms of glycaemic control compared to routine diabetes treatment (21). A recent small pilot study suggested that the implantation of the bypass device enhances secretion of incretin hormones such as glucagon-like peptide 1 (GLP-1), which might explain the improvement in glycaemic parameters observed. (22)

The potential advantages of the EndoBarrier[™] are that it is minimally invasive, can be inserted and removed endoscopically as an out-patient procedure under conscious sedation, and the putative costs are lower than with BS. However, long-term efficacy and safety data on a large number of patients implanted with the EndoBarrier[™] are lacking.

In addition, the detailed mechanisms of improved metabolic control induced by the EndoBarrier[™] device as well as the impact on gut peptides or gut microbiota are largely unknown. As changes in gut microbiota have been suggested to be associated with changes in gut permeability, subsequent low-grade chronic inflammation and insulin resistance as well as glycaemia (23), the impact of this device on gut microbiome composition needs to be further elucidated, as it is very likely that it impacts gut microflora. Moreover, although an effect on glucose control and incretin levels was shown after the EndoBarrier[™] implantation, data on sustainability of these effects after removal of the device are not yet available.

5. AIMS OF THE STUDY

The aim of the study is to explore short and longer-term effects of the EndoBarrier[™] implantation on insulin resistance and beta-cell function assessed by repeated Botnia clamps. In addition we will determine the changes in gut peptides and gut permeability after implantation of a removable duodeno-jejunal bypass device in obese subjects with sub-optimally controlled type 2 diabetes. Further we aim to investigate the changes in body weight and body composition and the change in global cardiovascular risk from baseline to 9 months, estimated using the UKPDS risk engine.

6. OBJECTIVES

6.1 Primary objective

Comparison of the changes in insulin sensitivity and beta-cell function following EndoBarrier[™] implantation in patients with type 2 diabetes and suboptimal glycaemic control and a BMI between 30 and 49kg/m².

6.2 Secondary objectives

- To assess the beta cell insulin response to oral and intravenous glucose loads early (4 weeks) and 9 months after EndoBarrier[™] implantation as well as 6 months after removal of the duodeno-jejunal bypass device.
- To assess changes in body weight from baseline to 9 and 15 months, respectively.
- To determine changes in gut permeability and gut microbiota from baseline to 9 and 15 months, respectively.
- To investigate changes in incretin hormone levels during the meal tolerance test (MTT) from baseline to 9 and 15 months, respectively.
- To evaluate changes in area under curve (AUC) of glucose from baseline to 9 and 15 months, respectively.
- To assess changes in body composition assessed by dual energy x-ray absorptiometry (DEXA) from baseline to 9 and 15 months, respectively.
- To evaluate correlations between MTT and Botnia clamp results regarding insulin sensitivity and beta-cell function
- To determine changes in cardiovascular risk as assessed by the UKPDS risk engine from baseline to 9 months and 15 months, respectively.

7. OUTCOMES

7.1 Primary outcome measures

 Acute insulin response to glucose during IVGTT will be used as a primary variable characterizing the beta cell function. Insulinogenic index (IGI), the early insulin response (EIR) and the ratio of AUC for C-peptide divided by AUC for glucose (AUC_{CP}/AUC_{GLU}) will be calculated.

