14 STATISTICAL CONSIDERATIONS

14.1 Calculations

The combination of MTT and IVGTT will allow a comprehensive assessment of different aspects of beta cell function along with reliable measures of insulin sensitivity assessed during the euglycaemic clamp procedure (30).

From MTT data, the following empirical indices of beta cell function will be derived: a) insulinogenic index (IGI) calculated as (30 min insulin – basal insulin)/(30min glucose – basal glucose); b) the early insulin response (EIR) calculated using formula (30 min insulin – basal insulin)/(30 min glucose)(31) or c) ratio of AUC for C-peptide divided by AUC for glucose (AUC_{CP}/AUC_{GLU}). AUCs are determined by trapezoidal method. Additionally, we intend to implement the established mathematical modeling to describe distinct features of beta cell function (30, 32-34). The model describes the relationship between insulin secretion and glucose concentration coupled with a model of C-peptide kinetics. It provides not only basal insulin secretion rate and total insulin secretion during OGTT, but also three important indices of dynamic properties of beta cell function: beta cell sensitivity to glucose (glucose sensitivity), beta cell sensitivity to the rate of change of glucose (rate sensitivity) and a potentiation factor (representing relative potentiation of insulin secretion throughout the OGTT).

Based on IVGTT measurements, the incremental trapezoidal area of insulin and C-peptide during the first 10 min after glucose administration represents the first-phase insulin response or acute insulin response (AIR). AIR will be also measured as the sum of insulin and C-peptide concentrations during the first 10 min after the glucose challenge. The incremental insulin/C-peptide secretion during the last 50 min of IVGTT represents the second-phase insulin secretion. The C-peptide deconvolution will be applied to reconstruct insulin secretory rates independently of insulin clearance.

Medizinische Universität Graz

It has been proved that rate sensitivity derived from OGTT is correlated to AIR calculated from IVGTT and it is therefore a valuable marker of first phase insulin secretion (34). AIR and rate sensitivity as well as insulin secretion rates are intended to be used for evaluation of beta cell insulin response to oral vs. intravenous glucose load.

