In 2010, a duodenal-jejunal bypass liner (DJBL, Endobarrier[™], GI Dynamics, Lexington, Massachusetts, USA) was introduced and CE marked. The EndoBarrier[™] is a 60 cm long impermeable fluoropolymer sleeve-like device, which is placed endoscopically via oral route and anchored in the duodenum creating a duodenal-jejunal bypass for a maximum of 12 months. It allows transit of chyme from the stomach through the jejunum without any contact to the duodenal mucosa. Both bile and pancreatic exocrine secretions do not get in contact with chyme in the proximal jejunum, thus the DJBL mimics a duodenal-jejunal bypass and therefore induces weight loss.

A number of studies demonstrated the feasibility of implanting this device with subsequent weight reduction[12-16]. In T2DM subjects, significant improvements in glycaemic parameters after EndoBarrier[™] implantation were observed as well as an improvement of insulin resistance measured by Homeostatic model assessment – insulin resistance (HOMA-IR) [17, 18].

However, thorough investigation of insulin resistance and beta-cell function with the gold standard, namely an intravenous glucose tolerance test combined with a hyperinsulinaemic-euglycaemic clamp (Botnia clamp) is lacking so far. The aim of the current study is to explore short and longer-term effects (26 weeks after removal) of the EndoBarrier[™] implantation on insulin resistance and beta-cell function assessed by repeated Botnia clamps to further delineate mechanisms of this intervention.

As the ENDO trial investigating the effects of the Endobarrier[™] device compared to a sham intervention was terminated early due to a higher rate of hepatic abscesses than expected, speculations about reasons are ongoing. A leaky gut and changes in the upper gastrointestinal microbiome caused by the bypass-liner are discussed. Therefore, another aim of this study is to investigate potential changes in microbiome composition and gut permeability.

Research objectives

Primary objectives

The primary objective of this trial is to determine the changes in insulin sensitivity and betacell function after EndoBarrier[™] implantation during a follow up of a 36-week period in patients with T2DM and a BMI between 30.0 and 49.0 kg/m².

Secondary objectives

- To assess the beta cell insulin response to oral and intravenous glucose loads early (4 weeks) and 36 weeks after EndoBarrier[™] implantation as well as 26 weeks after removal of the duodeno-jejunal bypass device.

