- Previous GI surgery that could affect the ability to place the device or the function of the implant
- GLP-1 receptor agonist therapy

- Known ischaemic heart disease or heart failure
- History of stroke
- Active Helicobacter pylori (Note: Subjects may be enrolled if they had a prior history of Helicobacter Pylori and were successfully treated)
- Actual iron deficiency anemia
- Subjects or Family history of a known diagnosis or pre-existing symptoms of systemic lupus erythematosus, scleroderma, or other autoimmune connective tissue disorder
- Known malignancy or any other multimorbid patient condition or circumstance, which, in the opinion of the investigator, would affect the patient's ability to participate in the protocol or would put the participant at an unjustified risk

Clinical endpoints

Primary endpoints

- Change in the glucose infusion rate (Botnia Clamp) adjusted for body weight at baseline from baseline to 4 and 36 weeks after the Endobarrier implantation, respectively
- Change in early insulin response from baseline to 4 and 36 weeks after the Endobarrier implantation, respectively

Secondary endpoints

- Change in the glucose infusion rate (Botnia Clamp) adjusted for body weight at baseline from baseline to 24 weeks after the Endobarrier explantation
- Change in early insulin response from baseline to 24 weeks after the Endobarrier explantation, respectively
- Change in body mass index from baseline to 4 and 36 weeks after the Endobarrier implantation and 24 weeks after the Endobarrier explantation
- Change in body weight from baseline to 4 and 36 weeks after the Endobarrier implantation and 24 weeks after the Endobarrier explantation
- Change in HbA1c from baseline to 4 and 36 weeks after the Endobarrier implantation and 24 weeks after the Endobarrier explantation
- Change in lactulose/mannitol ratio from baseline to 4 and 36 weeks after the Endobarrier implantation and 24 weeks after the Endobarrier explantation
- Change in glucose AUC (MMT) from baseline to 4 and 36 weeks after the Endobarrier implantation and 24 weeks after the Endobarrier explantation
- Change in c-peptide AUC (MMT) from baseline to 4 and 36 weeks after the Endobarrier implantation and 24 weeks after the Endobarrier explantation
- Change in UKPDS CHD risk from baseline to 4 and 36 weeks after the Endobarrier implantation and 24 weeks after the Endobarrier explantation

Sample Size

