This study is planned as a mechanistic pilot trial to gather first data about the parameter outlined in the primary and secondary parameter section. Currently, insufficient data are available on parameters for estimating the sample size required for this pilot trial. However, previous pilot trials investigating measurements of glucose metabolism with EndoBarrier[™] have used 10-16 subjects to demonstrate improvements[25, 26]. Therefore, we aim to include 10 subjects in our trial.

Statistical Analyses

Time of statistical analysis

All statistical analyses will be performed after the completion of trial and dataset closing.

Analysis population

All analyses will be performed on the 'Intention to treat (ITT)' or 'full analysis set' population. All patients who will be randomized to treatment sequences will be considered for the ITT analysis.

Data inspection

Data will be received in Microsoft Excel format and will be imported into statistical softwares for the analysis. First, data will be inspected for data entry errors on 10% of randomly selected data. Afterwards, data will be inspected for outliers and implausible values and these data points will be verified from the clinical report forms.

Summarization of data

Qualitative variables will be summarized as frequency with corresponding percentage (%), while quantitative variables will be summarized as either mean ± standard deviation (SD) or median and interquartile range (IQR) as appropriate. Both quantitative and qualitative variables will be presented in the table.

Statistical procedures

Normality of quantitative variables will be assessed using Shapiro-Wilk tests. The choice of statistical procedures for both primary and secondary quantitative endpoints will depend upon the distribution of variables. If normality assumption is violated, no data transformation will be carried out.

The early insulin response will be estimated from the MMT using the formula (30 minutes insulin – basal insulin)/(30 minutes glucose). The AUCs are determined by the trapezoidal method. Based on IVGTT measurements, the incremental trapezoidal area of insulin and C-

peptide during the first 10 minutes after glucose administration will represent the firstphase insulin response or acute insulin response (AIR). AIR will be also measured as the sum of insulin and C-peptide concentrations during the first 10 minutes after the glucose challenge.

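### The SAP makes meal-test early insulin response the only primary beta-cell endpoint and gives IVGTT acute insulin response, which the protocol named primary, no endpoint line and no visible explanation

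*Protocol*

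**What the plan says.** Protocol 7.1 (Primary outcome measures) gives primary status by name to one measure: "Acute insulin response to glucose during IVGTT will be used as a primary variable characterizing the beta cell function". It then lists the insulinogenic index, EIR and the C-peptide/glucose AUC ratio as indices to be calculated. Section 14.1 derives those three from the meal test and AIR from the intravenous glucose tolerance test (IVGTT), which is the first hour of the Botnia clamp.

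The SAP (Primary endpoints) has two lines. One is the weight-adjusted glucose infusion rate (GIR) from the clamp. The other is "Change in early insulin response from baseline to 4 and 36 weeks after the Endobarrier implantation, respectively". Under Statistical procedures the source of the second is explicit: "The early insulin response will be estimated from the MMT using the formula", namely the 30-minute insulin increment over 30-minute glucose. SAP EIR is therefore not AIR under another name. AIR appears in the SAP only as a definition in that same section.

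The SAP Introduction nevertheless sets out to study "insulin resistance and beta-cell function assessed by repeated Botnia clamps to further delineate mechanisms of this intervention", and the protocol Synopsis has the same aim: "implantation on insulin resistance and beta-cell function assessed by repeated Botnia clamps". SAP secondary objective 1 keeps both routes: "To assess the beta cell insulin response to oral and intravenous glucose loads early (4 weeks) and 36 weeks after".

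**The concern.** An analyst who follows the SAP reports EIR as the primary beta-cell result; a reader of the protocol expects AIR. In an open, single-arm study, an unexplained difference of this kind leaves readers unable to rule out that the outcome was selected.

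The two measures cannot stand in for each other. EIR follows an oral load, rests on a pre-meal and a 30-minute sample, and has glucose in the denominator. AIR follows an intravenous bolus, uses samples over ten minutes, and its incremental area has no glucose divisor. The protocol offers no basis for treating EIR as a proxy for AIR. The oral index that it ties to AIR is a different one: "It has been proved that rate sensitivity derived from OGTT is correlated to AIR calculated from IVGTT". The SAP does not mention rate sensitivity. Protocol 14.1 also gives AIR a role in the oral versus intravenous comparison: "AIR and rate sensitivity as well as insulin secretion rates are intended to be used for evaluation of beta cell insulin response".

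Two parts of the SAP's own aims are left without a listed endpoint: the beta-cell half of the Botnia-clamp aim, and the intravenous part of secondary objective 1.

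**Working it through.** Neither document gives a power, effect size or standard deviation for AIR or EIR, so there is no planned figure to reproduce. The check is a side-by-side reading and a count.

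**Status of each measure**

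| Measure | Test | Protocol | SAP |
|---|---|---|---|
| AIR | IVGTT, 0–10 min | Named as a primary variable (7.1) | Defined only; no endpoint line |
| EIR | Meal test, 0 and 30 min | Under the 7.1 heading, to be calculated | Primary (weeks 4, 36) and secondary (post-explantation) |
| GIR | Clamp, last 60 min | Insulin sensitivity measure (14.1) | Primary and secondary |

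**Endpoint lines in the SAP**
- Primary: GIR, EIR = 2.
- Secondary: GIR, EIR, BMI, weight, HbA1c, lactulose/mannitol ratio, glucose AUC, C-peptide AUC, UKPDS coronary risk = 9.
- Total 2 + 9 = 11. IVGTT-derived: 0. The GIR lines use the clamp phase, and both AUC lines use the meal test. EIR: 2 lines. AIR: 0.

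**Primary contrasts**
- As written: 2 endpoints × 2 time points = 4, of which GIR 2, EIR 2, AIR 0.
- AIR added and EIR kept primary: 3 × 2 = 6.
- AIR added and EIR moved to secondary: 2 × 2 = 4.

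**Versions of AIR left open.** Protocol 14.1 and the SAP allow insulin or C-peptide, each as an incremental area or a sum: 2 × 2 = 4 versions, or 4 × 2 = 8 possible contrasts at weeks 4 and 36. One named version gives 2.

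**The incremental area also needs a baseline.** With samples 2 minutes apart and baseline value B, the incremental insulin area is

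I(0) + 2[I(2) + I(4) + I(6) + I(8)] + I(10) − 10·B.

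Protocol 11.2 samples at both −10 and 0 min. Taking B as the mean of the two rather than I(0) changes the area by 10·{I(0) − [I(−10) + I(0)]/2} = 5·[I(0) − I(−10)]. Naming the area without defining B does not fix one number.

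**Are the data there?** Insulin and C-peptide at 0, 2, 4, 6, 8 and 10 min are 6 time points at each of 4 clamp visits (V2, V5, V7, V9): 6 × 4 = 24 per subject, with the −10 min sample in addition. AIR can be computed at every planned time point without new sampling.

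**Limits on the contrast between the measures.** The liner alters the oral route only while in place. The week-36 meal test is at V8, after removal at V7, so that argument applies to week 4 only. Both loads are dosed per kilogram of body weight (protocol 11.1, 11.2), so weight scaling does not separate the measures.

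**The case against.** The strongest reply is that the SAP imported nothing new. EIR was already under the protocol's primary heading, and the protocol calls AIR one primary variable, not the only one. This is an unpowered pilot meant to gather first data, and no sample size rests on which beta-cell index is labelled primary. This stands, and it lowers the severity. It does not reconcile the documents: the measure singled out by name in 7.1 has no endpoint line.

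A reader might infer that AIR has been dropped. The documents do not support that. The SAP still defines AIR, its repeated-measures ANOVA or Friedman test for parameters over time could cover it, and the endpoint list is not exhaustive: body composition, the microbiome and the meal-test/clamp correlations are objectives without a line too. The count of 0 in 11 shows missing status, not that AIR will go unanalysed.

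A reader might also infer outcome switching after a look at the data. The SAP cites a 2018 publication while the protocol's latest citations are from 2013, so the SAP appears to be the later document. Neither document gives a study start date, and nothing shows that data had been seen. The absence of a reason is also limited to the visible text: the amendment history has a heading but no content, and front pages were removed.

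Nor does the whole Botnia-clamp aim lack an endpoint. GIR serves the insulin-resistance half, and the SAP's formal primary objective does not name the clamp.

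Finally, section 7.1 does not require EIR to be demoted, and neither document ranks insulin above C-peptide for AIR.

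**Conclusion.** The mismatch holds. The SAP's only primary beta-cell endpoint is meal-test EIR, and AIR, which the protocol named as a primary variable, has no primary or secondary line, no time points and no main version. Both primary beta-cell contrasts are EIR. The beta-cell half of the clamp aim and the intravenous part of secondary objective 1 have no listed endpoint.

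This should be fixed, but it does not invalidate the plan. The conclusion rests on the visible text of both documents and assumes that an endpoint line is what gives a measure its reporting status. It does not rest on any claim about when data were seen.

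**What to change.** In the SAP:

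1. Add to the primary endpoints: change in AIR over 0–10 min of the IVGTT, baseline versus weeks 4 and 36. Add AIR at the post-explantation visit to the secondary endpoints.
2. Name one main version of AIR and label the others supportive. The incremental insulin area is one example; if it is chosen, define its baseline from the −10 and 0 min samples. If C-peptide is preferred, say so.
3. State whether EIR stays co-primary or becomes secondary. Either is compatible with reconciling the documents. If both stay primary, say that the primary contrasts rise from 4 to 6.
4. Whichever option is taken, give the date and reason for the difference from the protocol and say whether data had been seen. Report AIR as the variable the protocol named primary. Restoring AIR is itself a change to the SAP, so this disclosure is needed in both cases.

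The cost is SAP wording plus that disclosure. AIR is already defined and the samples are already scheduled at all 4 clamp visits, so no new visit, sample or assay is needed. Keeping both measures primary adds 2 contrasts.
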